3.5 Secondary Study Endpoints

The other secondary endpoints regarding pruritus will be assessed at baseline and as follows:

1. Percentage of patients with an improvement in weekly average PNRS 3 from baseline. This will be assessed at week 6,12,18
2. Percentage of patients with an improvement in weekly average PNRS 4 from baseline. This will be assessed at week 6,12,18
3. Mean change in the verbal rating scale (VRS) of pruritus as measured 0=none; 1= mild; 2=moderate; and 3=severe/intense. This will be assessed at week 6,12,18
4. Mean change of 5D pruritus score. This is a multidimensional questionnaire designed to assess the degree, duration, direction, disability and distribution of pruritus longitudinally with scoring ranging from 5=no pruritus/well-controlled to 25=severe pruritus/poorly controlled. This will be assessed at baseline and at week 18.
5. Chronic Liver Disease Questionnaire (CLDQ). This is a validated quality life instrument for patients with chronic liver disease evaluating systemic symptoms, fatigue, physical activity, emotional function, and worry using a 7 point scale with 1=all of the time; 2=most of the time; 3=a good bit of the time; 4=some of the time; 5=a little of the time; 6=hardly any of the time; and 7=none of the time. This will be assessed at baseline and week 18.

3.6 Primary Safety Endpoints

This is an exploratory efficacy study with no specific primary safety endpoint. Adverse events will be tracked and reported using Good Clinical Practice standards and as described in Section 8 of this protocol.

Page 10 of 29

[name]

[name]

[name], DO

CONFIDENTIAL

The safety of dupilumab in this population will be assessed by evaluating the detailed medical history through physical examination, vital signs, and clinical laboratory testing. Concomitant medications and procedures will be collected from time of informed consent to the end of the study.

3.7 Identification of Source Data

The following source data will be directly recorded on the Case Report Form (CRF):

- Screening and documentation of adverse events
- Confirmation of patient counseling and education
- PNRS score
- VRS score
- 5D Pruritus Score
- CLDQ questionnaire

The following source data will not be directly recorded in the CRF, but will be captured in supportive documentation to include study source documents and the EMR:

- Laboratory results and clinical interpretation of the values

4 Subject Selection Enrollment and Withdrawal

4.1 Inclusion Criteria

Subjects who meet the following criteria will be considered eligible to participate in the clinical study:

1. Male and/or female subjects 18 years or older with chronic pruritus of moderate to severe severity in the setting of intrahepatic or extrahepatic cholestatic liver disease. Chronic is defined as greater than 6 weeks of symptom duration. Pruritus severity is based on the peak pruritus numerical rating score of 4 (moderate severity).
2. Documentation of a personally signed and dated informed consent indicating that the subject or their legally acceptable representative has been informed of all pertinent aspects of the trial.
3. Willingness and ability to comply with scheduled clinic visits, physical exams, laboratory tests, questionnaires, effective contraception use, and other trial procedures.

4.2 Exclusion Criteria

Subjects who meet one or more of the following criteria will not be considered eligible to participate in the clinical study:

1. Male and/or female subjects under 18 years of age.
2. Pruritus due to a primary inflammatory skin dermatosis or other forms of psychogenic pruritus utilizing skin biopsies as needed.
3. Pregnant females

4. History of intrahepatic cholestasis of pregnancy
5. Any form of chronic hepatic pruritus associated with underlying malignancy
6. Liver transplant recipients
7. Allergy to dupilumab or its ingredients
8. Inability to provide informed consent
9. Concomitant use of selective opioid antagonists
10. Subjects with severe asthma (requiring high-dose inhaled or systemic corticosteroids)
will be excluded from the study.
11. Patients with known helminth infections

4.3 Subject Recruitment, Enrollment and Screening

Subjects will be recruited from a single, tertiary-care facility from the principal investigator and/or co-investigator clinical practices located in the departments of dermatology, gastroenterology and hepatology, and transplantation at Mayo Clinic in Florida. Potential subjects will be screened to confirm a diagnosis of chronic hepatic pruritus based on clinical evaluation and documentation of inclusion/exclusion criteria. Patients will be provided with a Research Participant Consent and Privacy Authorization Form describing the study drug, protocol, inclusion and exclusion criteria, as well as risks and benefits of participation.

4.4 Early Withdrawal of Subjects

4.4.1 When and How to Withdraw Subjects

Patients are free to withdraw at any time and for whatever reason. No data will be collected for withdrawn subjects. Withdrawn subjects may be replaced within the accrual period. There will be no follow-up for withdrawn subjects. Pre-specified reasons for discontinuing include, but are not limited to, the following:

- Patient Request: Patient decided that he/she did not want to continue (for any reason)
- Sponsor/Principal Investigator Request: Patients may be withdrawn from the study for any reason, at the discretion of the Sponsor/PI.
- Adverse Event: Patient experienced a related or unrelated event that would interfere with the study objectives/evaluation
- Lost to Follow-up: Patient did not come in for a visit and could not be reached by phone
- Treatment Failure: If in the Principal Investigator and/or Investigators' judgment, the patient's condition required another form of treatment
- Inclusion/Exclusion Discrepancy/Violation: Patient should not have been enrolled
- Noncompliance: Patient is not complying with the protocol requirements (i.e. visit schedule, dosing, regimen, etc.); a patient is to be withdrawn if he/she misses two consecutive visits
- Other: Any other reason

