4.4.2 Data Collection and Follow-up for Withdrawn Subjects

If a participant withdraws from the study, no additional attempts will be made to contact the participant.

5 Study Drug

Dupilumab is FDA approved to treat adults with moderate-to-severe atopic dermatitis (eczema) that is not well controlled with prescription therapies used on the skin (topical), or who cannot use topical therapies. Dupilumab can be used with or without topical corticosteroids. It is not known if Dupilumab is safe and effective in children with atopic dermatitis under 18 years of age.

Dupilumab is FDA approved to treat adults with other asthma medicines for the maintenance and treatment of moderate-to-severe asthma in people aged 12 years and older whose asthma is not controlled with their current asthma medicines. Dupilumab helps prevent severe asthma attacks and may also help reduce the amount of oral corticosteroids need while preventing severe asthma attacks. Dupilumab is not used to treat sudden breathing problems. It is not known if Dupilumab is safe and effective in children with asthma under 12 years of age.

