Preexisting Condition

A preexisting condition is one that is present at the start of the study. A preexisting condition should be recorded as an adverse event if the frequency, intensity, or the character of the condition worsens during the study period.

General Physical Examination Findings

At screening, any clinically significant abnormality should be recorded as a preexisting condition. At the end of the study, any new clinically significant findings/abnormalities that meet the definition of an adverse event must also be recorded and documented as an adverse event.

Post-study Adverse Event

All unresolved adverse events should be followed by the sponsor-investigator until the events are resolved, the subject is lost to follow-up, or the adverse event is otherwise explained. At the last scheduled visit, the sponsor-investigator should instruct each subject to report, to the sponsor-investigator, any subsequent event(s) that the subject, or the subject's personal physician, believes might reasonably be related to participation in this study.

Abnormal Laboratory Values

Any clinical laboratory abnormality that can reasonably be related to the administration of dupilumab should be documented as an adverse event.

Hospitalization, Prolonged Hospitalization or Surgery

Hospitalization, prolonged hospitalization, or surgery is to be reported as an adverse event if it can reasonably be related to use of dupilumab.

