8.2 Recording of Adverse Events

At each contact with the subject, the study team will seek information on adverse events by specific questioning and, as appropriate, by examination. Information on all adverse events should be recorded immediately in the source document, and also in the appropriate adverse event section of the case report form (CRF). All clearly related signs, symptoms, and abnormal diagnostic, laboratory or procedure results will be recorded in the source document.

All adverse events occurring during the study period will be recorded. The clinical course of each event should be followed until resolution, stabilization, or until it has been ultimately determined that the study treatment or participation is not the probable cause. Serious adverse events that are still ongoing at the end of the study period must be followed up, to determine the final outcome. Any serious adverse event that occurs during the Adverse Event Reporting Period and is considered to be at least possibly related to the study treatment or study participation should be recorded and reported immediately.

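### Sections 4.4.1 and 4.4.2 stop all data collection, follow-up and contact at withdrawal, which conflicts with the Section 8 duty to follow an adverse event that is still open

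*Combined protocol and SAP*

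**What the plan says.** Section 4.4.1 sets two rules for withdrawn subjects: "No data will be collected for withdrawn subjects" and "There will be no follow-up for withdrawn subjects". Its list of reasons for discontinuing then includes:

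- Adverse Event: "Patient experienced a related or unrelated event that would interfere with the study objectives/evaluation".
- Treatment Failure: in the investigators' judgment the patient's "condition required another form of treatment".
- Lost to Follow-up, as a separate reason: "Patient did not come in for a visit and could not be reached by phone".

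Section 4.4.2 adds: "If a participant withdraws from the study, no additional attempts will be made to contact the participant".

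Section 8 says something different. Under Post-study Adverse Event, 8.1 states: "All unresolved adverse events should be followed by the sponsor-investigator until the events are resolved", with two further ways for follow-up to end: the subject is lost, or the event is explained in some other way. Section 8.2 states: "The clinical course of each event should be followed until resolution, stabilization, or until it has been ultimately determined" that treatment or participation is probably not the cause. It makes follow-up to a final outcome mandatory for serious events still ongoing when the study period ends. Neither section exempts withdrawn subjects.

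**The concern.** A coordinator dealing with a subject withdrawn because of an adverse event finds one section that forbids follow-up and another that asks for it. If 4.4.1 is applied as written, the rule is selective. A subject who completes treatment with an open event is followed under Section 8, while a subject whose event led to withdrawal is not.

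What is at stake is the outcome of those events: whether they resolved, when, and whether that followed stopping the drug. Section 8.3.1 asks for these items on the adverse event form. Section 1.6 itself relies on such information when it describes recovery from conjunctivitis and keratitis in earlier trials. The investigators may still see the course of an event in their own clinics, since 4.3 recruits from their practices, but 4.4.1 gives no route for that information into the study data.

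**Working it through.** No arithmetic applies. Section 7.1 reports no formal power analysis, and the plan gives no expected rate of withdrawal or of adverse events in this population. The check is to apply both sets of rules to each kind of subject.

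| Subject | Sections 4.4.1 and 4.4.2 | Sections 8.1 and 8.2 | Conflict? |
|---|---|---|---|
| Completes with an open event | Do not apply | Follow the event | No |
| Withdrawn for an adverse event, still open | No data, no follow-up, no contact | Follow the event | Yes |
| Withdrawn for an adverse event, already resolved | Same | Nothing left to follow | No |
| Treatment failure with worsened pruritus, unresolved | Same | 8.1 counts worsening of a preexisting condition as an adverse event, so follow it | Yes |
| Treatment failure through lack of improvement, no open event | Same | No event to follow | No |
| Withdrawn by the investigator for another reason, with an open event | Same | Follow the event | Yes |
| Leaves at own request with an open event | Same | Follow the event | Yes in the text, though the subject may decline contact |
| Cannot be reached | Same | 8.1 releases the duty | No under 8.1 |

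Three steps settle how to read the table.

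1. **Does the lost-to-follow-up exit in 8.1 remove the conflict?** No. Section 4.4.1 treats loss to follow-up as its own category, defined by failure to reach the patient. A subject withdrawn for an adverse event can usually still be reached.
2. **How strong is the duty in Section 8?** For most events the verb is *should*. For serious events ongoing at the end of the study period it is *must*. For a withdrawn subject, meeting that clause requires finding out whether the event is still ongoing, and 4.4.1 and 4.4.2 rule that out.
3. **What is lost?** Not onset: 8.2 has every event in the study period recorded, so an event open at withdrawal is already on file and counts toward the stopping consideration in 8.5. On the 8.3.1 form, resolution can be entered as unresolved at withdrawal, but the eventual outcome and its date cannot be obtained.

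The reach of 4.4.2 is also unclear. It could cover only subjects who themselves choose to leave, or all withdrawals. On the narrow reading the no-contact rule does not reach investigator-initiated withdrawals, but the two sentences in 4.4.1 still do.

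**The case against.** The strongest reply is that the sections have different jobs: 4.4.1 ends study visits and efficacy data, and Section 8 governs adverse events. There is text to support this. Section 3.6 says that events are tracked and reported under Good Clinical Practice and Section 8. Section 8.3 has the sponsor-investigator evaluate each identified event and decide what follow-up it needs. A sensible team may well work this way. This stands as a reason to expect less harm in practice. It does not settle the text: neither section mentions withdrawn subjects, and 4.4.1 bars data and follow-up without limiting either to efficacy.

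Other parts of the reply also stand, and they rule out stronger conclusions that a reader might draw:

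- *Every treatment-failure withdrawal breaches Section 8.* It does not. Lack of improvement is not an adverse event, and the conflict needs an event that is open at withdrawal.
- *Section 8 requires every event to be followed to resolution.* It does not. Stabilization, loss of the subject, another explanation, or a judgment that treatment is probably not the cause also end follow-up.
- *The gap can be measured by blank form fields or missed scheduled visits.* It cannot. The resolution field can be marked unresolved, and any withdrawal forgoes the remaining visits, with or without the fix.
- *The stopping rule or the efficacy results are compromised by this.* They are not, because onset is recorded. Section 3.6 also states that there is no specific primary safety endpoint.

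Respect for a subject's wish to leave is a fair argument for limiting contact after a request to withdraw. It does not justify a blanket bar that also covers withdrawals made by the investigator.

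**Conclusion.** The contradiction is real and confined to subjects withdrawn while an adverse event is open, including worsened pruritus behind a treatment-failure withdrawal. For them, 4.4.1 and 4.4.2 read literally leave the outcome uncollected, although 8.1 and 8.2 say it should be sought and, for ongoing serious events, must be.

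The number of such subjects cannot be estimated from the documents. It could be none; the planned enrolment is 12, and withdrawn subjects may be replaced. The conclusion assumes that staff apply 4.4.1 as worded. If they treat Section 8 as governing, the practical loss shrinks or disappears, but they would then be departing from 4.4.1. This is worth correcting because it concerns patient safety and the correction is cheap. It does not threaten the trial's efficacy conclusions.

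**What to change.** Add an exception to both 4.4.1 and 4.4.2: Section 8 continues to apply to any adverse event unresolved at withdrawal, including worsened pruritus. Follow-up is by phone or clinic record until one of the endpoints in 8.1 or 8.2 is reached, and the outcome and its date are recorded, unless the subject declines further contact. State in 4.4.2 whether the no-contact rule applies only to subjects who ask to leave. No change is needed to the analysis, the sample size or the stopping rule.

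The cost is a few calls or chart checks for each subject affected, and possibly matching consent wording. Some outcomes will stay unknown where contact is declined.

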4.4.2 Data Collection and Follow-up for Withdrawn Subjects

If a participant withdraws from the study, no additional attempts will be made to contact the participant.

5 Study Drug

Dupilumab is FDA approved to treat adults with moderate-to-severe atopic dermatitis (eczema) that is not well controlled with prescription therapies used on the skin (topical), or who cannot use topical therapies. Dupilumab can be used with or without topical corticosteroids. It is not known if Dupilumab is safe and effective in children with atopic dermatitis under 18 years of age.

Dupilumab is FDA approved to treat adults with other asthma medicines for the maintenance and treatment of moderate-to-severe asthma in people aged 12 years and older whose asthma is not controlled with their current asthma medicines. Dupilumab helps prevent severe asthma attacks and may also help reduce the amount of oral corticosteroids need while preventing severe asthma attacks. Dupilumab is not used to treat sudden breathing problems. It is not known if Dupilumab is safe and effective in children with asthma under 12 years of age.

5.1.1 Mechanism of Action

Dupilumab is a human monoclonal IgG4 antibody that inhibits interleukin-4 (IL-4) and interleukin-13 (IL-13) signaling by specifically binding to the IL-4Ra subunit shared by the IL-4 and IL-13 receptor complexes. Dupilumab inhibits IL-4 signaling via the Type I receptor and both IL-4 and IL-13 signaling through the Type II receptor. Blocking IL-4Ra with dupilumab inhibits IL-4 and IL-13 cytokine-induced inflammatory responses, including the release of pro-inflammatory cytokines, chemokines, nitric oxide, and IgE.

5.1.2 Pharmacodynamics

Consistent with receptor blockade, serum levels of IL-4 and IL-13 were increased following dupilumab treatment. The relationship between the pharmacodynamic activity and the mechanism(s) by which dupilumab exerts its clinical effects is unknown.

5.1.3 Pharmacokinetics

Absorption: Following an initial subcutaneous (SC) dose of 600 mg, dupilumab reached peak mean \pm SD concentrations (C_{max}) of 70.1 \pm 24.1 mcg/mL by approximately 1 week post dose. Steady-state concentrations were achieved by Week 16 following the administration of 600 mg starting dose and 300 mg dose either weekly (twice the recommended dosing frequency) or every other week. Across clinical trials, the mean \pm SD steady-state trough concentrations ranged from 73.3 \pm 40.0 mcg/mL to 79.9 \pm 41.4 mcg/mL for 300 mg administered every 2 weeks and from 173 \pm 75.9 mcg/mL to 193 \pm 77.0 mcg/mL for 300 mg administered weekly. The bioavailability of dupilumab following a SC dose is estimated to be 64%.

Distribution: The estimated total volume of distribution was approximately 4.8 ± 1.3 L.

Elimination: The metabolic pathway of dupilumab has not been characterized. As a human monoclonal IgG4 antibody, dupilumab is expected to be degraded into small peptides and amino acids via catabolic pathways in the same manner as endogenous IgG. After the last steady-state dose of 300 mg Q2W or 300 mg QW dupilumab, the median times to non-detectable concentration (<78 ng/mL) are 10 and 13 weeks, respectively.

Dose Linearity: Dupilumab exhibited nonlinear target-mediated pharmacokinetics with exposures increasing in a greater than dose-proportional manner. The systemic exposure increased by 30-fold when the dose increased 8-fold following a single dose of dupilumab from 75 mg to 600 mg (i.e., 0.25times to 2-times the recommended dose).

Weight: Dupilumab trough concentrations were lower in subjects with higher body weight.

Immunogenicity: Development of antibodies to dupilumab was associated with lower serum dupilumab concentrations. A few subjects who had high antibody titers also had no detectable serum dupilumab concentrations.

Specific Populations:

Geriatric Patients

In subjects who are 65 years and older, the mean \pm SD steady-state trough concentrations of dupilumab were 69.4 ± 31.4 mcg/mL and 166 ± 62.3 mcg/mL, respectively, for 300 mg administered every 2 weeks and weekly. No dose adjustment in this population is recommended.

Renal or Hepatic Impairment

No formal trial of the effect of hepatic or renal impairment on the pharmacokinetics of dupilumab was conducted.

Drug Interaction Studies: Drug interaction studies have not been conducted with dupilumab.

5.2 Treatment Regimen

All study participants will receive dupilumab 600 mg SC at week 0; then 300 mg SC every 2 weeks for a total of 18 weeks.

5.3 Method for Assigning Subjects to Treatment Groups

This is an open-label pilot investigation and all study participants are assigned to active treatment. There is no placebo arm in this study.

5.4 Preparation and Administration of Study Drug

The study drug will be stored and dispensed at the first study visit from the Mayo Clinic Research Pharmacy in Jacksonville, FL. Subsequent doses of the study drug will be self-administered by the subject until completion of the study.

For subjects willing and able to self-administer or have a caregiver administer the study drug outside the clinic, the study staff will train the subject/caregiver on preparation and administration of study drug. Subjects who prefer to have clinic staff administer study drug may choose to have injections administered in the clinic.

The procedure for preparing the dupilumab dose for SC injection will be provided in the pharmacy manual. Subcutaneous injection sites should be alternated among the different quadrants of the abdomen, upper thighs, and upper arms, so that the same site is not injected for 2 consecutive weeks. To allow for adequate assessment of possible injection site reactions (ISRs), study drug should be administered only into areas of normal-looking skin. Instructions for recording and reporting of ISRs will be provided in the study reference manual.

Detailed instructions for transport, storage, preparation, and administration of study drug will be provided by the site to the patient (or caregiver).

